### 20.3 Duration of storage

Specimens and data will be stored indefinitely.

### 20.4 Access to data and/or specimens

Access to specimens collected under the current study will be limited to the PI and select members of the IPM staff.

## 22.0 Confidentiality, Privacy and Data Management

See the Research Data Plan Review Form

### II. Study Overview

- A. **Brief Description of the Purpose of the Study**— The overall goal of this project is to compare the effectiveness of a six-month Mindfulness-based stress reduction (MBSR) intervention versus stress management education (SME) in improving glucose control and other important outcomes in patients with uncontrolled diabetes (HbA1c  $\geq 7.5\%$ ).
- B. **Adherence Statement**— The Data Safety Monitoring Board Chair will carry out this Data Safety Monitoring Plan (DSMP) independent of the study and in adherence to the protocol approved by the Penn State Hershey IRB.

[name] updates to the National Center for Complementary and Integrative Health (NCCIH) DSMP template v.3.0 to meet CONSORT Harms Criteria were adapted in this DSMP (Ioannidis et al., 2004).

### III. Confidentiality

#### A. Protection of Subject Privacy

During this study, all of the materials (e.g., biometric data, surveys, biologic specimens) collected are for research purposes only, and data will be kept in strict confidence. No information will be given to anyone without permission from the subject. Confidentiality will be ensured by use of identification codes. All data, whether generated in the laboratory or at the study visit, will be identified with an identification code unique to the subject.

#### B. Database Protection

The database will be secured with password protection. The informatics manager will receive only coded information that is entered into the database under those identification numbers. Electronic communication with outside collaborators will involve only unidentifiable information. Source documents including all paper and electronic records for all enrolled subjects, i.e., case report forms, laboratory reports, subject study binders, etc. will also be secured. Electronic source documents will be secured with password protection. Paper source documents will be kept in locked files in the Investigators' academic office.

As part of the Penn State Clinical and Translational Science Institute (CTSI), Penn State is a member of the Research Electronic Data Capture (REDCap) Consortium. Study data, including questionnaires and lab data, will be managed using REDCap which is a secure web application designed to support data capture for research studies, providing user-friendly web-based case report forms, real-time data entry validation (e.g., for data types and range checks), audit trails and a de-identified data export mechanism to common statistical packages (SPSS, SAS, Stata, R/S-Plus). The data management system will allow research staff to register participants, generate participant visit schedules, enter data, edit entry errors, and determine entry status of participant forms. Database access for REDCap is granted on a study-by-study basis. At the start of the trial when the database is created all research personnel will be given defined user roles and assigned a unique username and password. Using the REDCap database management application, each new participant will be registered into the trial.

registry. The registry will assign a unique identification (ID) number to the participant that links his/her data across multiple tables. REDCap allows for data type and range checks at the point of data entry and provides clear alerts for valid entry ranges or types. In addition to the range checks built into REDCap at the point of data entry, extreme outliers and missing data for our primary and secondary outcomes as well as baseline demographic and clinical characteristics will be queried by the biostatisticians prior to data analysis to ensure completeness and accuracy of our reported data. REDCap was developed by a multi-institutional consortium, which includes Penn State, and was initiated at Vanderbilt University. The database is hosted at the Penn State Health Hershey Medical Center and College of Medicine data center, which will be used as a central location for data processing and management.

The research coordinator, who is blinded to group assignment, will enter the subject data into the REDCap database. The SME instructors, who are not involved in the collection or analysis of outcomes, will randomize subjects using the REDCap randomization module. The REDCap randomization module will be set up so that only the SME instructor or other unblinded research staff members who need to access randomization information will have role rights and exporting rights to ensure blinding.

### **C. Confidentiality During Adverse Event (AE) Reporting**

AE reports and annual summaries will not include subject or group-identifiable material unless requested by the DSMB due to safety concerns. Each report will only include the identification code.

## **IV. Adverse Event Information**

### **A. Definition**

An adverse event (AE) is any untoward medical occurrence in a subject temporally associated with participation in the clinical study or with use of the experimental agent being studied. An adverse finding can include a sign, symptom, abnormal assessment (laboratory test value, vital signs, electrocardiogram finding, etc.), or any combination of these.

A Serious Adverse Event (SAE) is any AE that results in one or more of the following outcomes:

- Death
- A life-threatening event
- Inpatient hospitalization or prolongation of existing hospitalization
- A persistent or significant disability/incapacity
- A congenital anomaly or birth defect
- Important medical event based upon appropriate medical judgment

### **B. Classification of AE Severity**

AEs will be labeled according to severity, which is based on their impact on the patient. Severity grade will be determined as 1 = Mild, 2 = Moderate, 3 = Severe, 4 = Very Severe, or 5 = Death according to the Common Terminology Criteria for Adverse Events (CTCAE) and other sources for grading the severity of adverse events. Severity seriousness will be determined as Serious or Not Serious. Seriousness, which requires a different reporting procedure is defined according to the Office for Human Research Protections, Guidance on Reviewing and Reporting Unanticipated Problems Involving Risks to Subjects or Others and Adverse Events (Linden, 2013; OHRP, 2007; NCI, 2017). These classifications will be determined using a specific set of external criteria with precise definitions provided by [name] who is independent from the study team and does not have a conflict of interest (See Severity Grading Tool in Appendix C1). The descriptions and grading scales

found in the revised NCI Common Terminology Criteria for Adverse Events (CTCAE) version 5.0 will also be utilized for AE reporting ([http://ctep.cancer.gov/protocolDevelopment/electronic\\_applications/ctc.htm](http://ctep.cancer.gov/protocolDevelopment/electronic_applications/ctc.htm)).

### C. AE Attribution Scale (Relatedness)

To assess the relationship of an event to the study intervention, the following guidelines are used:

1. Related (Possible, Probable, Definite)
  - a. The event is known to occur with the study intervention.
  - b. There is a temporal relationship between the intervention and event onset.
  - c. The event abates when the intervention is discontinued.
  - d. The event reappears upon a re-challenge with the intervention.
2. Not Related (Unlikely, Not Related)
  - a. There is no temporal relationship between the intervention and event onset.
  - b. An alternate etiology has been established.

AEs will be categorized according to the likelihood that they are related to the study intervention. Specifically, they will be labeled as "0 = Not related, 1 = Unlikely related, 2 = Possibly related, 3 = Probably related, or 4 = Definitely related. Additionally, we will use [name] of Previously-Reported Meditation Effects (See Appendix C2) to determine whether the symptom is an expected effect, and to determine the symptom Domain out of 8 domains including a Diabetes Domain (See Appendix D) in addition to [name] 7 domains (Affective, Cognitive, Conative, Perceptual, Sense of Self, Social, and Somatic).

Relatedness to treatment will be assessed according to 8 causality and relatedness criteria that regulatory agencies such as the World Health Organization (WHO), the Federal Drug Administration (FDA), and the National Institutes of Health (NIH) use to make health policy decisions (NIH, 2016; Agbabiaka et al., 2008; Turner, 1984; WHO, 2016). These criteria are designed to assess treatment-relatedness in individual cases in the absence of prospective or epidemiological (base rate) data. The 8 standard causality/relatedness criteria are 1) prior published reports, and expert judgment, 2) subjective attribution, 3) temporal proximity (challenge), or exacerbation, 4) consistency, 5) dose-response gradient 6) de-challenge, 7) re-challenge, 8) specificity, (Turner, 1984; Naranjo, 1986; Naranjo, 1982; Naranjo, 1981; Hill, 1965; Hill, 2015; Gallagher et al., 2011; Theophile et al., 2010).

The Relatedness Criteria Definitions table below provides detailed definitions for assessing relatedness in individual cases.

Relatedness Criteria Definitions Table	
1. Previous Reports/known effects and expert judgment	Symptom has been previously reported in association with meditation or judged to be caused by meditation by experts (meditation teachers/clinicians)
2. Subjective attribution	Participant thinks symptom was caused by meditation
3. Temporal proximity OR Exacerbation	Symptom occurred for the first time OR pre-existing symptoms got worse during/following treatment
4. Consistency	More than one occasion following meditation
5. Dose/gradient	Symptom was worse with higher dose of treatment
6. De-challenge	Decreased when stopped meditation
7. Re-challenge	Re-appeared or increased when meditation restarted

8. Specificity	Presence of plausible alternative cause: Something other than meditation (medical illness, life event, substances) could account for symptom (meditation played no causal role).
----------------	--

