**Blinding:**

The PI, research coordinators and all other research team members involved in the collection or review of outcomes data will be blinded. The random assignment of subjects to MBSR or SME will not be communicated to any research team member who will be collecting or reviewing outcomes data. The subjects, SME instructors, MBSR instructors, data manager, video coders, [name] will be asked to keep the study group assignments concealed from the blinded investigators and study personnel.

The SME instructors, MBSR instructors, and other unblinded research team members will be asked not to reveal the number of study subjects in an MBSR course, or in an SME course, to the research coordinators and other blinded research team members.

The research coordinators and other blinded research team members will be:

- Blinded to the number of subjects randomized to MBSR in a cohort/wave
- Blinded to the number of subjects randomized to SME in a cohort/wave

The research coordinators and other blinded research team members will be:

- Aware of the total number of subjects randomized in a cohort/wave

Subjects will be asked to keep their study group assignment concealed from the blinded study personnel, including the research coordinators and other study personnel that they meet during the study visits. At the beginning of any phone call, study visit, or other contact with a subject, blinded research team members will remind subjects not to say anything that would reveal their group assignment e.g. instructors' names, specifics about their classes or Daily Diary survey questions, the PSU Zoom link for their classes, etc.

The research coordinators and other blinded research team members will not have access to the Experience Sampling Surveys in REDCap, which will be managed by unblinded research team members e.g. the SME instructors. Additionally, the PSU Zoom links for the classes will only be available to [name] and the instructors as these individuals will not be blinded.

Procedures in the MBSR group will parallel procedures in the SME group to maintain blinding. As an example, since subjects in the MBSR group are not allowed to continue with MBSR if they miss Orientation, the same will apply for subjects in the SME group. Additionally, if a session for one group needs to be canceled for any reason, the concurrent session for the other group will also be canceled.

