After Class #8, subjects will start receiving emails inviting them to participate in additional MBSR or SME Retreat sessions and monthly booster sessions. The monthly booster sessions in months 3 to 6 (Booster sessions #1 to 4) are required sessions for the study. The remaining booster sessions, and any additional Retreat sessions after Class #8, are optional sessions subjects may choose to participate in if they wish. Attendance will be recorded at these additional sessions, however subjects will not receive any financial compensation for participating in the optional sessions. By keeping subjects informed of additional MBSR or SME booster and Retreat sessions after Class #8, these emails will be important for subject retention in the study.

We will be comparing MBSR alone versus SME alone. The MBSR group will not receive SME. The SME group will not receive any mindfulness.

**MBSR and SME Home Practice:** Subjects in both the MBSR and SME groups will be asked to do at least 25 to 30 minutes of home practice per day for 6 out of 7 days per week. Positive clinical outcomes and high adherence have been reported with 25 to 30 minutes per day of MBSR home practice, which is a common adaptation to the standard 45 minutes per day of MBSR home practice.

Home practice in MBSR will consist of mindfulness activities in accordance with the standard MBSR curriculum. Home practice in SME will consist of listening to excerpts of audiobooks about general stress management or nutrition facts.

Instructors will assign home practice for the first 7 weeks of MBSR and SME, starting after Class #1. There will be no home practice assignments after Class #8, however after Class #8 subjects will be encouraged to continue their home practice activities regularly on their own. The Daily Diary survey will be administered daily throughout the study to measure the type and quantity of home practice.

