## Adverse Events Form

Specifically, the research coordinator will use the Adverse Events Form which includes the CTCAE and accompanying documents (Severity Grading Tool and List of Previously-Reported Meditation Effects in the Appendices, and the Relatedness Criteria Definitions Table above in section IV-C) to provide:

- a) A description of the AE/SAE, including the Adverse Event/CTCAE (To document COVID-19 related adverse events, the CTCAE term "Infections and infestations - Other, specify" will be entered. A text box will branch allowing the research coordinator to specify the other condition. The research coordinator will enter "COVID-19" here).
- b) MedDRA System Organ Class (SOC)
- c) Adverse Event Domain (as categorized in the List of Previously-Reported Meditation Effects in Appendix C2, and in the Diabetes Domain Expected Events in Appendix D).
- d) Start and end dates
- e) Severity grading (1 = Mild, 2 = Moderate, 3 = Severe, 4 = Very Severe, 5 = Death) based on the CTCAE and the Severity Grading Tool (Appendix C1)
- f) Relationship to treatment (using the Relatedness Criteria Definitions Table above in section IV-C and the List of Previously-Reported Meditation Effects in Appendix C2). (0 = Not related, 1 = Unlikely related, 2 = Possibly related, 3 = Probably related, 4 = Definitely related)
- g) Action taken (if any) by study team regarding study intervention (0 = None, 1 = Study intervention modification, 2 = Study intervention discontinued)
- h) Treatment required for this adverse event (0 = None, 1 = Medication, 2 = Hospitalization, 3 = Other (specify):\_\_\_\_\_)
- i) Outcome of AE (as assessed after 2 weeks or next check-in time point) (1 = Resolved, 2 = Recovered with minor sequelae, 3 = Recovered with major sequelae, 4 = Ongoing/Continuing treatment, 5 = Condition worsening, 6 = Death and 7 = Unknown)
- j) Expectedness (1 = Yes, 2 = No) (Refer to List of Previously-Reported Meditation Effects in Appendix C2)
- k) Seriousness (1 = Yes, 2 = No) (See Severity Grading Tool for definition of Serious Adverse Event (SAE); use Serious Adverse Events Form if event is Serious)

**Serious Adverse Events Form** will capture:

- a) The date the subject reported the SAE
- b) SAE onset date (The date of onset for an SAE is the date the outcome of the AE fulfilled one of the serious criteria).
- c) SAE diagnosis date (In some cases this will be the same as the onset date).
- d) SAE stop date

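### Six of the eight adverse-event relatedness criteria refer to meditation but are applied to both arms, so SME events cannot meet four of them, and the answers needed could unblind staff

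*Combined protocol and SAP*

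**What the plan says.** DSMP section IV.C first gives guidelines for judging an event's relation to the study intervention: known occurrence, timing, abatement on stopping and return on re-challenge. None of these names an arm. It then sets a 0 to 4 scale and refers to the Relatedness Criteria Definitions Table for detailed definitions.

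In that table, criterion 1 is "Symptom has been previously reported in association with meditation or judged to be caused by meditation by experts", criterion 2 is "Participant thinks symptom was caused by meditation", criterion 4 is "More than one occasion following meditation" and criterion 6 is "Decreased when stopped meditation". Criterion 7 asks about return once meditation was resumed. Criterion 8 asks about a plausible cause other than meditation, with illness, life events and substances as examples. Only criteria 3 ("pre-existing symptoms got worse during/following treatment") and 5 (dose) speak of treatment.

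The table is used for every event. Under Adverse Events Form, "the research coordinator will use the Adverse Events Form which includes the CTCAE and accompanying documents", and the table is one of those documents. The SAE form and the Stress Experience Survey follow-up (DSMP E.3.1) also use it. No SME version is given.

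On the control arm, protocol section 7.2.4 states: "The SME group will not receive any mindfulness". On blinding, the same section states: "The PI, research coordinators and all other research team members involved in the collection or review of outcomes data will be blinded".

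**The concern.** Relatedness should mean the same thing in both arms of a trial with an active control. SME has content that could plausibly cause events: gentle stretching with a resistance band, a 7-hour retreat and home practice on most days. Protocol section 10.0 lists injury from exercise as a risk and warns of hypoglycemia during or after the stress reduction sessions in either program. If the definitions fit only one program, the same clinical picture can be rated differently according to arm.

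Two things are at stake. The first is reporting. DSMP section IV.F sets the 7-day and 15-day NIH deadlines for serious, unexpected events related to the intervention, and protocol section 18.1 sends to the IRB harms judged unexpected and probably related. The second is blinding. The coordinator phones subjects to document events, administers two surveys, and helps subjects obtain the home HbA1c reading. Several rows cannot be completed without knowing whether the subject meditated.

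**Working it through.** The plan gives no figure to reproduce. The check is a count of the table's rows, followed by a trace of who applies them.

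**Step 1. Classify the eight rows.**

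| Criterion | Refers to | Can an SME-caused event meet it as worded? |
|---|---|---|
| 1 Previous reports | meditation | Yes, if the symptom is on the Appendix C2 list |
| 2 Subjective attribution | meditation | No |
| 3 Timing or exacerbation | treatment | Yes |
| 4 Consistency | meditation | No |
| 5 Dose | treatment | Yes |
| 6 De-challenge | meditation | No |
| 7 Re-challenge | meditation | No |
| 8 Specificity | meditation | Counts against: read literally, SME is something other than meditation |

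Rows naming meditation: 1, 2, 4, 6, 7, 8, so 6/8 = 75%. Neutral rows: 3 and 5, so 2/8 = 25%.

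**Step 2. Count the criteria that support relatedness.** Criterion 8 works against relatedness, which leaves 8 − 1 = 7. An SME-caused event in a subject who does no meditation loses 2, 4, 6 and 7, so at most 7 − 4 = 3 remain (1, 3 and 5). An event caused by meditation in the MBSR arm can meet all 7.

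**Step 3. Compare the table with its parent section.** Take a hypothetical SME subject whose shoulder pain starts after stretching, stops when she skips sessions and returns when she resumes. The IV.C guidelines on timing, abatement and re-challenge are all met. In the table, the stopping and restarting do not count because no meditation was stopped or restarted. Criterion 8, read literally, supplies an alternative cause, and IV.C lists an established alternate etiology under not related. The guidelines and the table therefore point in different directions for one event.

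**Step 4. Trace the blinding.** Rows 2, 4, 6 and 7 turn on whether the subject meditated, stopped or restarted. The protocol treats answers of this kind as capable of revealing the arm. Section 7.2.3 hides Counterfactual Measurement responses from coordinators for that reason. Section 7.2.3 also keeps daily-diary data from blinded staff, and section 7.2.2 keeps the open-ended attrition answer from them. For the adverse-event interview the only safeguard described is the general reminder to subjects not to disclose their group.

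**Step 5. Identify the rater.** The Adverse Events Form section and E.3.1 give the relatedness rating to the coordinator. Protocol section 9.3 says a medically licensed investigator makes all AE assessments. These passages are not reconciled. If that investigator is the PI, the blinding problem moves rather than disappears, because the PI is blinded too.

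**The case against.** The strongest case on the other side is that this is loose drafting with little consequence. Two rows and all the IV.C guidelines are neutral. No rule converts the eight criteria into the 0 to 4 scale or requires a minimum count, so a sensible rater can still call an SME event related. Criterion 8's examples can be judged in either arm. E.3.1 has subjects asked about relatedness to the intervention, not to meditation. All subjects are told that meditation is one possible activity, so the word itself reveals nothing. Section 8.3 plans no comparison of related events by arm, and DSMB tables are pooled. Events are recorded whatever their relatedness, and unrelated SAEs are still reported, less urgently. HbA1c is a laboratory value or a displayed kit reading and most questionnaires are self-administered, which limits the effect of unblinding on efficacy data.

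Most of this stands, and it rules out several stronger readings:

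- A reader might infer that the table is worded only for meditation, or that SME events can hardly be rated related. Rows 3 and 5, the symptom-based row 1 and the IV.C guidelines contradict both.
- A reader might infer a definite bias toward finding MBSR events related. The documents do not establish the direction. Appendix C2 is broad, including pain, headache, fatigue and sleep changes, and a blinded rater could use it to over-attribute SME events.
- A reader might infer that the coordinator must ask questions that reveal the arm, or that each interview unblinds. No passage scripts such questions. The risk lies in the answers.

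The objection does not remove the mismatch: the forms require a table that, as written, gives SME events fewer ways to qualify. Pooled DSMB tables also mean that unequal attribution would not be visible during the trial.

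**Conclusion.** The point holds as a defect in the definitions. Six of eight criteria name meditation, four of the seven supporting criteria are closed to events caused by SME, and criterion 8 read literally counts SME as an alternative cause. This conflicts with the neutral guidelines in the same section and makes the rating that feeds NIH and IRB reporting unequal between arms. It affects the planned 145 SME subjects.

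The effect on the number of events rated related cannot be calculated, because the plan gives no event rates and no rule from criteria to rating. The net direction is uncertain. The unblinding risk is possible but unquantified; it rests on staff seeking the information that rows 2, 4, 6 and 7 need. The conclusion assumes that the table is applied as written and that SME subjects do no meditation as part of their program, as the protocol intends.

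**What to change.** - In criteria 2, 4, 6, 7 and 8, replace meditation with the assigned study program (sessions or home practice).
- Let criterion 1 cover known effects of either program.
- Use the same neutral wording on the AE and SAE forms and in the follow-up questions to subjects, so that no answer needs to name the activity.
- Reconcile protocol section 9.3 with the Adverse Events Form section and E.3.1 on who rates relatedness.

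The Appendix C2 expectedness check can stay with blinded staff. It only compares a symptom with a list and needs no knowledge of the arm.

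The cost is DSMP and form wording only.
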